### 2.2.2 Clinical Studies

ANB019-001, a first in human Phase I study in healthy subjects and subjects with psoriasis has been conducted (ANB019-001 2018).

The Single Ascending Dose (SAD) part of the study enrolled 48 healthy adults and has been completed. Six dose levels were administered to 8 subjects in each cohort: 10 mg, 40 mg, 100 mg, 300 mg, and 750 mg by IV injection and 100 mg by SC injection. After single dose administration, ANB019 was generally well tolerated in male and female healthy adults 18-43 years old. Overall, 40 subjects (83%) experienced at least one treatment-emergent adverse event (TEAE). The percentage of subjects who experienced at least 1 TEAE was similar across treatment groups: 29 subjects, 81% in ANB019 group and 11 subjects, 92% in placebo. The most commonly reported AEs were upper respiratory tract infection (URTI) (28% ANB019, 50% placebo), headache (28% ANB019, 25% placebo), viral URTI (11% ANB019, 8% placebo), oropharyngeal pain (8% ANB019, 0% placebo), nausea (8% ANB019, 0% placebo), tension headache (6% ANB019, 8% placebo), gastroenteritis (6% ANB019, 0% placebo), herpes simplex (6% ANB019, 0% placebo), acne (6% ANB019, 0% placebo), and catheter site pain (6% ANB019, 0% placebo). All other SAEs occurred as single events. The majority of TEAEs were mild (73%) and moderate (26%) in severity with exception of 1 severe AE of elevated creatine kinase deemed unrelated to study treatment. No subject discontinued the study due to AE. There were no SAEs reported in the SAD portion of the study. No clinically relevant abnormalities were noted in vital signs, physical examinations, electrocardiograms (ECGs), or laboratory parameters.

One subject with PP was enrolled and completed the study as per protocol. This subject received a single dose of 750 mg by IV injection. The PP cohort was removed from the study and no further subjects were enrolled. No TEAEs were reported for the subject with PP in the SAD part of the study.

Treatment-related effects observed in the 13-week, repeat-dose toxicity study included protozoa in the stomach, an increase in nonformed feces and prolapsed rectum observations, the latter was not dose-related. The increase in protozoa in the stomach has been observed in monkeys treated with immune-modulating drugs (Augey 2006) and is consistent with the putative mechanism of action of ANB019. The increased incidence of protozoa, nonformed feces and prolapsed rectum were not considered adverse as they responded to veterinarian intervention. Gastrointestinal infections are clinically monitorable and, in the case of most protozoa, are readily treatable even in the context of immunocompromised individuals (Farthing 2006). One female monkey receiving 60 mg/kg ANB019 IV was found moribund on Study Day 34. The cause of the moribund nature was not determined and had an uncertain relationship to ANB019 but could be due to treatment-related immune-modulation. However, data published on IL-36 R deficient humans shows no deleterious effect on general health and normal immune function broadly preserved, indicating that inhibition of IL-36 R, apart from disease modification, does not compromise host defenses. Similar to other immune-modulating treatment paradigms, subjects should be closely monitored for any gastrointestinal clinical manifestations including infections and evaluated on ongoing basis. If a gastrointestinal infection is suspected, the subject should be treated as clinically indicated.

As allergic or anaphylactic reactions may occur in subjects treated with mAbs, subjects should be observed during and after study drug administration. Subjects with true allergic/anaphylactic reactions should not receive further doses of the product.

As ANB019 is an mAb, based on clinical studies with other mAbs, study participants may experience symptoms of an apparent allergic reaction to the drug, also known as ‘cytokine release syndrome.’ The symptoms of this vary dramatically but can include:

- Mild to moderate fever, chills, headache, nausea, and vomiting.

- Moderate to severe signs and symptoms such as edema, hypotension, and pulmonary infiltrates (eg, blood and mucus in the lung).

Such reactions should be managed as clinically indicated and according to standard clinical practice.

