### **6.1 Study Treatment Administered**

Eligible subjects will receive 750 mg of ANB019 IV in an open-label manner followed by 3 doses of 100 mg SC administered on Days 29, 57, and 85.

Due to the potential for infusion reactions with protein drugs, ANB019 should be administered in an environment under close supervision of a physician and where full resuscitation facilities are immediately available. Allergic/anaphylactic reactions and infusion-related reactions typically begin during, or within several hours of dose administration. The onset of symptoms may be rapid, and some reactions may be life-threatening. The study treatment should be immediately stopped and permanently withdrawn in case of severe allergic/anaphylactic reactions. For treatment of allergic reactions, current local standard of care guidelines should be followed.

Study treatment details are provided in Table 1.

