### **6.6 Dose Modification**

No dose modification is allowed in this study. Study treatment can be interrupted temporarily only once or permanently if deemed necessary as per the Investigator's discretion. Refer to [Section 7.1](#).

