#### **7.1.1 Temporary Interruption**

Only one dose of study treatment may be interrupted temporarily in the case of an AE per the Investigator's discretion. The Medical Monitor and the Sponsor should be informed of all details pertaining to the decision. Study drug may be resumed at the next scheduled dosing visit after discussion with the Medical Monitor. In the case of a recurring or new AE after study treatment has resumed, the subject will be early terminated. If a clinically significant finding is identified (including, but not limited to changes from baseline) after enrollment, the Investigator or qualified designee will determine if any change in subject management is needed. Any new clinically relevant finding will be reported as an AE.

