#### **7.1.2 Re-challenge**

Not applicable for this study.

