## 8.0 STUDY ASSESSMENTS AND PROCEDURES

- Study procedures and their timing are summarized in Section 1.3.
- Protocol waivers or exemptions are not allowed.
- Immediate safety concerns should be discussed with the Medical Monitor and the Sponsor or designee immediately upon occurrence or awareness to determine if the subject should continue or discontinue in the study.
- Adherence to the study design requirements, including those specified in the Schedule of Activities (see Section 1.3), is essential and required for study conduct.
- All screening evaluations must be completed and reviewed to confirm that potential subjects meet all eligibility criteria. The Investigator will maintain a screening log to record details of all subjects screened and to confirm eligibility or record reasons for screening failure, as applicable.
- Procedures conducted as part of the subject’s routine clinical management (eg, blood count) and obtained before signing of the ICF may be utilized for screening or baseline purposes provided the procedures met the protocol specified criteria and were performed within the time frame defined in the Schedule of Activities (see Section 1.3).
- The maximum amount of blood collected from each subject over the duration of the study, including any extra assessments that may be required, will not exceed 204 mL. Repeat or unscheduled samples may be taken for safety reasons or for technical issues with the samples.

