### **8.3.6 Adverse Events of Special Interest**

The following events are considered AESI in this study.

- Serious infection (requiring hospitalization; or with fatal outcome or sepsis; or requiring IV antibiotics/antimicrobials).
- Serious allergic reaction.
- Gastrointestinal clinical manifestations including infections.

All AESI, including follow-up, should be reported in an expedited manner. (Please follow procedures for AE/SAE recording and reporting outlined in [Appendix 4](#)).

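### Section 2.3 bars further ANB019 after a true allergic reaction, but the dosing and resumption rules in Sections 6.1 and 7.1.1 do not carry that bar

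*Protocol*

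**What the plan says.** The rules on dosing after an allergic reaction are spread over several protocol sections. The SAP sets no dosing rule.

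- **2.3 Benefit/Risk Assessment:** "Subjects with true allergic/anaphylactic reactions should not receive further doses of the product". The visible text attaches no severity limit.
- **6.1 Study Treatment Administered:** "The study treatment should be immediately stopped and permanently withdrawn in case of severe allergic/anaphylactic reactions". For treating allergic reactions it refers to local standard of care, and it gives no dosing rule for those that are not severe.
- **6.6 Dose Modification:** "Study treatment can be interrupted temporarily only once or permanently if deemed necessary", at the Investigator's discretion.
- **7.1.1 Temporary Interruption:** one dose may be interrupted for an AE, with the Medical Monitor and the Sponsor informed. Then: "Study drug may be resumed at the next scheduled dosing visit after discussion with the Medical Monitor". Allergic reactions are not excepted. It adds: "In the case of a recurring or new AE after study treatment has resumed, the subject will be early terminated".
- **7.1.2 Re-challenge:** "Not applicable for this study".
- **8.0 Study Assessments and Procedures:** "Immediate safety concerns should be discussed with the Medical Monitor and the Sponsor or designee immediately upon occurrence or awareness".
- **4.5.1 and 7.2** set individual stopping and withdrawal criteria that turn on judgment. Neither names allergic reactions.

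**The concern.** One safety decision, whether to dose again after an allergic reaction, has an uneven threshold. Section 2.3 uses the kind of reaction (true allergic). Section 6.1 uses its intensity (severe). Section 7.1.1 uses neither and treats an allergic reaction like any other AE.

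A site deciding on the next dose will look first to the treatment and interruption sections, and these do not contain the bar that Section 2.3 sets. At stake is re-exposure of a subject whom the sponsor has already said should not be re-exposed.

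**Working it through.** No sample size, rate or test is involved, so the check is a comparison of the provisions against one case: a true allergic reaction of mild or moderate intensity.

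| Protocol section | Trigger | Consequence | Does it stop the next dose in this case? |
|---|---|---|---|
| 2.3 | True allergic/anaphylactic reaction | No further doses | Yes |
| 6.1 | Severe allergic/anaphylactic reaction | Permanent withdrawal | Not reached |
| 6.6 | Permanent stop judged necessary | Permanent stop | If so judged |
| 7.1.1, resumption | Dose interrupted for an AE | May resume after Medical Monitor discussion | Not by its terms; the discussion may stop it |
| 7.1.1, termination | Recurring or new AE after resumption | Early termination | Acts after a further dose has been given |
| 7.1.2 | None stated | Re-challenge not applicable | No rule either way |
| 4.5.1 | SAE, or clinically significant AE possibly due to drug, judged to warrant stopping | Dosing stopped | If so judged |
| 7.2, lead-in (hard to parse) | Significant AE the Investigator considers drug-related | Withdrawal | If judged significant |
| 7.2, first bullet | Before dosing, Investigator decides subject should be withdrawn or is at risk | Drug not given | If so judged |
| 8.0 | Immediate safety concern | Discussion with Medical Monitor and Sponsor | If seen as such |

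**Step 1: are *true* and *severe* the same threshold?** No. Appendix 4 grades intensity by effect on everyday activities: a moderate event interferes with them and a severe one prevents them. *True* in Section 2.3 appears to mark a kind of reaction. The paragraph that follows it deals with apparent allergic reactions of the cytokine-release type, which are to be managed clinically. A mild or moderate true reaction therefore falls within Section 2.3 but outside the withdrawal sentence in Section 6.1.

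**Step 2: follow the case to the next dose.** ANB019 is given on Days 1, 29, 57 and 85, so doses are 28 days apart (29 − 1 = 57 − 29 = 85 − 57 = 28). If the reaction resolves within that interval, no dose need be interrupted, and the discussion that Section 7.1.1 ties to resumption need not arise. If a dose is skipped, Section 7.1.1 allows resumption after that discussion.

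**Step 3: remove what other sections catch.** Severe reactions fall under 6.1. Reactions judged significant fall under 4.5.1 or 7.2. A subject judged at risk falls under the first bullet of 7.2. Anything seen as an immediate concern goes to the Medical Monitor and Sponsor under 8.0. What remains is a true allergic reaction that is not severe and is judged not significant. For that case Section 2.3 is the one provision that bars the next dose without a further judgment about significance or risk.

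**Step 4: size.** The available documents give no frequency of such reactions to ANB019, so no expected number or probability can be calculated.

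**The case against.** The strongest reply is that there is no contradiction. Section 6.1 does not say that withdrawal is limited to severe reactions or that other reactions may be re-dosed. Section 7.1.1 is permissive, general to all AEs, and routed through the Medical Monitor. An Investigator can obey 2.3, 6.1 and 7.1.1 together, and one who follows 2.3 breaks no rule. A true allergic reaction to ANB019 is drug-related by its nature, so under 7.2 the only open word is *significant*. The first bullet of 7.2 also blocks dosing of a subject judged at risk, and nothing confines it to the first dose. Appendix 2 requires each Investigator to sign after reading the whole protocol.

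Most of this stands. It rules out a head-on conflict and makes the exposed case small. It does not remove the unevenness: the safeguards outside 2.3 depend on a judgment of severity, significance, risk or urgency that 2.3 does not ask for.

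A reader might also infer that 7.1.2 prohibits re-challenge. It says only that the topic does not apply, which is not a ban. Nor is it an allowance.

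**Conclusion.** The point holds as a gap in alignment. The rule in Section 2.3 is not carried into Sections 6.1 and 7.1.1, and the case exposed is a non-severe true allergic reaction judged not significant.

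Two stronger readings are tempting and are not supported:

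- **That the protocol permits or directs re-dosing after allergic reactions.** No section directs it, and 2.3 forbids it.
- **That the scheduled doses remaining after a reaction measure the exposure.** That count would apply only if 2.3 were overlooked and 4.5.1, 7.2 and 8.0 all failed to catch the case. It describes the dosing calendar and not an effect of the wording.

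The conclusion assumes that *severe* in 6.1 carries its Appendix 4 meaning and that no text outside view qualifies the 2.3 rule. The heading and earlier part of Section 2.3 are not in the available text, so confidence is moderate.

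**What to change.** Make two one-sentence changes at the next amendment:

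- **Section 6.1:** state that any true allergic or anaphylactic reaction to ANB019, regardless of severity, requires permanent discontinuation of ANB019.
- **Section 7.1.1:** state that true allergic or anaphylactic reactions are excepted and that study drug may not be resumed after one.

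Infusion-related and cytokine-release reactions stay under Section 8.3.7 and clinical management. Whether a reaction is *true* remains the Investigator's judgment. Section 7.2 needs no change, because 7.1 already makes stopping treatment a discontinuation from the study.

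The price is that a subject with a mild true reaction loses the remaining doses and leaves the study, which 2.3 read with 7.1 already implies. Design, visits, endpoints and analyses are unaffected.

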### 3.0 OBJECTIVES AND ENDPOINTS

Objectives	Endpoints
Primary	

 
To evaluate the efficacy of ANB019 in subjects with active GPP as measured by the Clinical Global Impression (CGI) scale according to the modified Japanese Dermatology Association (JDA) severity index total score
 
	
 
Proportion of subjects achieving clinical response at Week 4 and Week 16. Clinical response is defined as “Very much improved,” “Much improved,” and “Minimally improved” on CGI scale according to modified JDA severity index total score
 

 
To assess the safety and tolerability of ANB019 in subjects with GPP
 
	
 
Assessment of AEs
 
Potentially significant and clinically important AEs, AESIs, SAEs, and AEs leading to withdrawal
 
Physical examinations
 
Vital signs
 
12-lead ECG
 
Clinical safety laboratory tests (hematology, biochemistry, and urinalysis)
 

Secondary	

 
To evaluate the effect of ANB019 on the total and individual skin lesion symptoms as measured by the modified JDA severity index score
 
	
 
Change in modified JDA severity index total skin lesions score (sum of erythema, erythema with pustules, edema) at all study visits
 
Change in affected BSA of erythema with pustules, erythema, and edema as measured by modified JDA severity index at all study visits
 

 
To evaluate the effect of ANB019 on total and individual components of systemic manifestations and laboratory findings as measured by modified JDA severity index score
 
	
 
Change in total and individual scores in systemic manifestations and laboratory findings as measured by modified JDA severity index at all study visits
 

 
To evaluate the effect of ANB019 on GPP using the GPPPGA
 
	
 
Proportion of subjects achieving a GPPPGA score of 0 or 1 at all study visits
 
Change from Baseline in GPPPGA scores at all study visits
 


 
To determine any treatment effect of ANB019 in PP (if present) as measured Psoriasis Area Severity Index (PASI)
 
	
 
Change in PASI score to evaluate a subject's overall PP disease state if present at all study visits
 

 
To assess the effect of ANB019 on the subject's quality of life
 
	
 
Change in Dermatology Life Quality Index (DLQI) total score at all study visits
 

 
To determine the PK of ANB019 in GPP subjects
 
	
 
Serum concentration following ANB019 administration
 
 
Following first dose administration of ANB019 these parameters will be determined:
 
 
<math>C_{max}</math>, <math>T_{max}</math>, AUC, and other parameters as appropriate
 

 
To test for immunogenicity to ANB019
 
	
 
Presence of ADA
 

Exploratory	

 
To explore the effects of ANB019 on skin biopsy biomarkers
 
	
 
Skin biopsies biomarkers (including but not limited to IL-17, IL-22, IL-8, dendritic cells, epidermal thickness, and leukocytes infiltration)
 

 
To assess the effect of ANB019 on inflammatory parameters such as serum cytokines including but not limited to IL-8
 
	
 
Change in serum cytokines as compared to baseline at Weeks 1, 4, 8, 12, 16, and 24
 

 
Provide photographic documentation of lesions
 
	
 
Photographic documentation of lesions
 

 
To explore GPP-associated mutations and additional pharmacogenomic analysis
 
	
 
Optional genetic testing (DNA and mRNA)
 

## 4.0 STUDY DESIGN

### 4.1 Overall Design

This is an open-label, single arm, multiple dose study to assess the clinical efficacy, as well as the safety, tolerability, and PK of multiple doses of ANB019 in subjects with GPP.

The screening period will be up to 42 days (6 weeks) prior to administration of study drug on Day 1. Written informed consent will be obtained from each subject prior to initiating any study related procedures. All screening procedures will be conducted in accordance with the Schedule of Activities (see Section 1.3).

On Day 1, subjects who meet the entry criteria will receive a 750 mg IV dose of ANB019 in an open-label manner followed by 3 doses of 100 mg SC administered on Days 29, 57, and 85. Subjects will leave the study center after completion of the 5 hours postdose assessments following IV administration and the 3 hours postdose assessments after the first and second SC injections and with the Investigator's approval. Subjects with any ongoing AEs or SAEs at the time of scheduled discharge from the study center should remain at the study center until the Investigator has determined that these events have resolved or are deemed as not clinically significant.

After completing Day 1 assessments, the subjects will return to the study center for follow-up visits on Days 3, 8, weekly from Day 8 to Day 29, and every other week up to Day 85, and monthly for 12 weeks to monitor changes in disease activity, safety, and tolerability. In addition, subjects will be contacted via phone by study staff to assess for safety (eg, AEs and changes in concomitant medications) on Days 36, 50, 64, and 78.

Subjects who are nonresponders will be early terminated 4 weeks after the 750 mg IV dose administration. A nonresponder is defined as:

- “No change” on CGI: 0 points change in JDA total score and not meeting “other criteria” for minimally improved.
- “Worsened” based on CGI:  $\geq 1$ -point increase in JDA total score.

Disease activity (response to study treatment) will be evaluated using the CGI scale according to the modified JDA severity index, change in total BSA as measured by modified JDA index affected by GPP, systemic manifestations and laboratory findings as per modified JDA severity index, GPPPGA scale, and PASI score (if PP is present). In addition, change in serum cytokines (including but not limited to IL-8) will be recorded. Quality of life (QoL) will be assessed using the DLQI.

Serum samples for PK and immunogenicity will be collected before the administration of ANB019 and at the other time points specified in the Schedule of Activities (see Section 1.3). Refer to Table 2 for additional information on sample collection and time points. All subjects

enrolled in the study will be asked to participate in the skin biopsy and/or genetic analysis; however, participation is optional and subjects will be asked to give specific consent for these assessments.

Safety assessments including AE/SAE monitoring, vital signs measurements, physical examination, ECGs, laboratory measurements, and urine assessments will be performed during the study.

The EOS visit will be on Day 169 and all subjects will return to the study center for the EOS procedures (see Section 1.3).

#### **4.2 Scientific Rationale for Study Design**

Currently there are no approved treatment modalities for use in subjects with GPP, and there is little evidence-based information to guide the management of this severe, life-threatening type of psoriasis.

In this context, the development of agents with new mechanisms of action is considered important for future clinical practice. This open-label single arm multiple dose study may provide evidence-based information about the clinical effect of this novel treatment.

#### **4.3 Justification for Dose**

ANB019 will be administered as a single IV dose of 750 mg followed by 3 doses of 100 mg SC administered on Days 29, 57, and 85.

The doses selected for this study have demonstrated favorable safety profile and prolonged pharmacodynamic activity in a Phase I study (ANB019-001). A loading dose of 750 mg IV will be administered on Day 1 to enable steady state concentration to be reached faster at initiation of the ANB019 100 mg SC dose. The 12-week treatment duration is expected to provide adequate time to assess the safety and efficacy of ANB019 in subjects with GPP.

